Participants in the FinSote 2020 Survey were adults aged 20 and over derived from the Digital and Population Data Services Registry, created in Jan 2020 after the merge between the Population Register of Statistics Finland and local register offices.²⁹ This sampling frame includes all residents in Finland. The survey was based on a stratified random sample of 22 regions (2000 adults aged 20-74, 800 adults aged 75+, total sample size 61600). Data collection started on September 14, 2020, and finished on February 8, 2021. Participants received a self-administered questionnaire in Finnish, Swedish, English or Russian, which could be returned on paper or filled in electronically. The analytical sample is 28199 participants, with a participation rate of 46%. In 2020, consent to linkage was included in the overall consent, and as a result, we were able to link all participants in the analytical sample.

We will link data from FinSote 2018 and 2020 surveys to the Finnish National Vaccination Register maintained by the Finnish Institute for Health and Welfare using a unique identifier assigned to all residents in Finland. The follow-up will be between December 27, 2020 (date of the first COVID-19 vaccination in the country) until May 31, 2022 or the latest available date.

Outcomes

Our primary outcome will be the vaccination uptake of at least two doses of a COVID-19 vaccine. We will examine four secondary outcomes:

- (i) vaccination uptake of at least one dose of a COVID-19 vaccine,
- (ii) vaccination uptake of the complete COVID-19 vaccination scheme (two doses and a booster dose),
- (iii) proportion of participants with more than 7 months between the first and second COVID-19 dose, and
- (iv) proportion of participants with more than 7 months between second dose and booster dose.

We will include any approved COVID-19 vaccination in Finland by the latest available date (i.e. April 29, 2022):³⁰ COVID-19 mRNA vaccines (Comirnaty and Spikevax), recombinant vaccines (Vaxzevria, COVID-19 vaccine Janssen, COVISHIELD, Nuvaxovid, COVOVAX), and inactivated vaccines (BIBP/Sinopharm, COVAXIN, Coronavac). Participants who have received the COVID-19 vaccine Janssen would be excluded from analyses on the second dose, as the vaccine only requires a single dose.

Exposures

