Effect modifiers

We will examine potential effect modification by reporting stratified results by age (as a categorical variable), sex and educational level.

Data sources and measurement

[figure not shown]
Data sources and measurements for all variables were described above. More details on the exact variables can be found in the Supplementary Appendix.

Bias

Confounding bias

We will reduce the risk of confounding by adjusting for potential confounders that causally precede the exposure and are associated with the outcome. We built a directed acyclic graph to guide the identification of potential confounders and mediators (Figure 1). Adjusting for mediators can result in an underestimation of the association and potentially introduce M-bias (a type of collider bias).^{31,32}

Figure 1. Directed acyclic graph of the causal association between tobacco use and COVID-19 vaccinations uptake

A special concern were participants who had a COVID-19 infection. Tobacco use is associated with COVID-19 infection and, in turn, having a COVID-19 infection can influence the willingness to vaccinate or delay COVID-19 vaccination. Current Finnish guidelines recommend to the general adult population, after having a COVID-19 infection, to: (i) wait at least two months before getting the first COVID-19 dose, (ii) wait at least four to six months after the COVID-19 infection or the first dose, whichever happens first. People with two doses will not be given a third dose if they have had COVID-19. Having a COVID-19 infection, according to our DAG, would act as a mediator. Excluding individuals who have had the infection (or adjusting for it) would result in estimating the direct effect between tobacco use and COVID-19 vaccination uptake and not the total effect. For this reason, our main analyses will report the outcomes without adjusting for having a COVID-19 infection. In sensitivity analyses, we will report estimates stratified by COVID-19 infection status and also we will use causal inference methods (e.g. marginal structural methods and G-formula) to account for this time-varying estimate. We expect, however, that this will not make a large difference, as the COVID-19 incidence prior to the start of the COVID-19 vaccinations was very low and continued to be low until the rise of the Omicron variant in mid-December 2021.³³ In practice, this means that a very small proportion of our sample will experience a COVID-19 infection during the study period.

Selection bias

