We described the categorisation of exposures and confounders above. We will model age as a continuous variable and tested non-linearity by comparing the linear model with penalised smoothing splines using a likelihood ratio test.³⁵ The variable years of education will be modelled as categorical to be able to account for secular changes in years of education during the study years. In other words, educational attainment increases over time and it is therefore more appropriate to calculate the educational attainment within each survey wave.

Statistical methods

We will use Poisson regression with robust standard errors to estimate the relative risk of confirmed COVID-19 cases. We will fit the following Poisson model:

$$(1) \quad \log \mu_i = \beta_0 + \beta_1 S_i + \beta_x X_i^* + \rho_1 R_a$$

where i denotes the individual, β_0 is the intercept; β_1 is the coefficient of interest for exposure to tobacco S ; a vector of covariates X^* (i.e., sex, age, marital status, years of education, mother tongue and participation in social activities); and fixed effects $\rho_1 R_a$ for wellbeing area a . We will report the exponentiated coefficient as the relative risk estimate for unadjusted and adjusted models with their corresponding 95% confidence intervals.

We will examine non-linearity between age and the outcome by comparing the linear model with penalised smoothing splines³⁵ using a likelihood ratio test with the Wald method.³⁶ We will use the model with splines if it performs better than the linear model, using a p-value of 0.05 as the threshold for this decision.

We will examine potential effect modification by reporting stratified analyses by age, sex and educational level. If there are noticeable differences, we will test for multiplicative interactions between tobacco use and sex, age and educational level by including an interaction term in equation 1. We will introduce the interaction terms one by one for each of the examined interactions. We will use a likelihood ratio test to compare the model with and without the interaction. A p-value lower than 0.05 in the likelihood ratio test will be used as an indication of the presence of an interaction. If there is evidence of an statistically significant interaction, we will include the interaction term in the final model.

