Our primary method to handle missing data will be multiple imputation, given that a missing at random assumption is the most likely in our data. We will examine patterns of missing data and use multiple imputation using chained equations (MICE). This procedure will be combined with the survey design tools to take the complex sampling design into account.

In sensitivity analyses, we will report estimates using complete case analyses (i.e. taking only the complex sampling design into account). We will also report the same estimates as the main analyses, but restricting the follow-up time to when vaccination coverage reached 60% and 80%. This will allow us to understand whether these associations changed over time and also provide estimates that might be comparable to countries with lower vaccination coverage, thus increasing the external validity of our estimates.

We will analyse the data using R version 4.1.1 and include the statistical code as a Supplementary Appendix.

References

- 2 Davies, N. G. *et al.* Estimated transmissibility and impact of SARS-CoV-2 lineage B.1.1.7 in England. *Science* **372**, eabg3055, doi:doi:10.1126/science.abg3055 (2021).
- 3 Campbell, F. *et al.* Increased transmissibility and global spread of SARS-CoV-2 variants of concern as at June 2021. *Euro Surveill* **26**, doi:10.2807/1560-7917.Es.2021.26.24.2100509 (2021).
- 4 Suthar, A. B. *et al.* Public health impact of covid-19 vaccines in the US: observational study. *BMJ* **377**, e069317, doi:10.1136/bmj-2021-069317 (2022).
- 5 Krause, P. R. *et al.* SARS-CoV-2 Variants and Vaccines. *New England Journal of Medicine* **385**, 179-186, doi:10.1056/NEJMsr2105280 (2021).
- 7 Kuodi, P. *et al.* Association between vaccination status and reported incidence of post-acute COVID-19 symptoms in Israel: a cross-sectional study of patients tested between March 2020 and November 2021. *medRxiv*, 2022.2001.2005.22268800, doi:10.1101/2022.01.05.22268800 (2022).

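### In the supplied text, the two dose-spacing outcomes have no risk set, minimum follow-up or rule for a next dose never received, so the relative risk, mainly for (iv), can be biased in either direction

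*Combined protocol and SAP*

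**What the plan says.** The Outcomes section defines (iii) as the "proportion of participants with more than 7 months between the first and second COVID-19 dose" and (iv) as the "proportion of participants with more than 7 months between second dose and booster dose". The only related restriction is that Janssen recipients "would be excluded from analyses on the second dose". That is a product rule. It does not define a risk set by earlier dose, and it does not name (iv).

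Setting and participants starts follow-up on 27 December 2020 and runs it "until May 31, 2022 or the latest available date". Statistical methods gives one model for all outcomes: "We will use Poisson regression with robust standard errors". Equation 1 has no offset, follow-up term or censoring. Missing data are to be multiply imputed, but the text does not say whether an interval with no second date counts as missing. A sensitivity analysis repeats the main estimates, "restricting the follow-up time to when vaccination coverage reached 60% and 80" per cent. The dose is not named and nothing is said about the spacing outcomes.

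On infection, the Confounding bias section reports that "People with two doses will not be given a third dose if they have had COVID-19". It then plans: "In sensitivity analyses, we will report estimates stratified by COVID-19 infection status", together with G-formula methods. Data sources and measurement refers to a Supplementary Appendix for variable details. That appendix is not in the supplied text.

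**The concern.** An interval between two doses is seen only if the second of them falls before follow-up ends. Read literally, a person boosted at 8 months is delayed, while a person still unboosted at 10 months is not. Each possible reading has its own distortion:

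- **(a) Recipients of both doses only.** The interval is right-truncated. People vaccinated late can contribute only short intervals, and people still waiting drop out.
- **(b) All recipients of the earlier dose, no next dose coded not delayed.** People still waiting after 7 months are misclassified.
- **(c) All recipients of the earlier dose, no next dose coded delayed.** People not yet 7 months past the earlier dose are miscounted.

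If smokers and non-smokers differ in when they had dose 2, or in whether they complete the series, the relative risk mixes that difference with delay. The introduction names spacing as one of two new contributions and leaves the direction of association open, so an artefact of either sign could be reported as a finding.

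**Working it through.** The plan gives no expected relative risk or power figure to reproduce, so the check starts from its coverage figures and dates.

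**From the documents.** Adult coverage on 14 June 2022 (introduction): 89.7% first dose, 87.6% second, 65.1% booster.

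- Two-dose adults without a booster: (87.6 − 65.1)/87.6 = 25.7%.
- First-dose adults without dose 2: (89.7 − 87.6)/89.7 = 2.3%.
- 31 May 2022 is 520 days, or 17.1 months, after 27 December 2020. Seven months earlier is about 31 October 2021 (month 10.1).

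By share of people, (iv) is the outcome mainly exposed. Outcome (iii) is not immune. Assume smokers are 15% of the sample, 95–96% of first-dose smokers get dose 2, and 1–5% of intervals are long. Coding a missing dose 2 as delayed then gives a relative risk of 1.27 to 2.09 with equal spacing among completers.

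**Illustration for (iv); all inputs below are assumed.** Dose 2 falls at time T ~ Normal, mean month 5, 6, 7 or 8, SD 1.5 or 3. The booster interval is 4 months plus an exponential wait with one rate r for both groups, so delay is equal and the unbiased relative risk is 1.00. The rate is solved so that 65.1/87.6 = 74.3% of two-dose recipients are boosted by 14 June 2022 (month 17.5). This gives r = 0.163 to 0.261 per month at SD 1.5 and 0.176 to 0.316 at SD 3. Let F(g) = 1 − exp(−r(g − 4)) for g above 4 and zero otherwise, and let C = 17.1.

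- (a) = E[max(F(C−T) − F(7), 0)] / E[F(C−T)]
- (b) = E[max(F(C−T) − F(7), 0)]
- (c) = 1 − E[F(C−T)] + (b)
- Next dose not received within 7 months, among those with 7 months of follow-up = 1 − F(7) = exp(−3r)

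Relative risk under (a), unadjusted, when smokers' mean dose-2 month is shifted by one month:

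| Shift | SD | Mean 5 | 6 | 7 | 8 |
|---|---|---|---|---|---|
| later | 1.5 | 0.92 | 0.88 | 0.82 | 0.74 |
| later | 3 | 0.93 | 0.91 | 0.89 | 0.87 |
| earlier | 1.5 | 1.06 | 1.09 | 1.13 | 1.22 |
| earlier | 3 | 1.06 | 1.08 | 1.10 | 1.12 |

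Across the same cells (b) runs from 0.65 to 0.86 (later) and 1.12 to 1.33 (earlier), and (c) from 1.00 to about 1.09 and 0.94 to 1.00. The redefined outcome does not depend on T, so it gives 1.00 under any timing shift. A recalculation reproduced these values to within 0.01.

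**Completion only.** Keep timing equal, let n₀ = 10% of non-smokers never be boosted, and put n₁ 5, 10 or 20 points higher in smokers. Under (b) the relative risk is (1 − n₁)/(1 − n₀) = 0.85/0.90, 0.80/0.90, 0.70/0.90 = 0.94, 0.89, 0.78. Under (a) it stays at 1.00. For the redefined outcome it is [1 − (1 − n₁)(1 − exp(−3r))] / [1 − (1 − n₀)(1 − exp(−3r))]. With r recalibrated (0.211 to 0.456) this gives 1.04–1.11, 1.08–1.23 and 1.16–1.45.

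**Coverage cut-offs.** If coverage means two doses, the share of eventual two-dose recipients already 7 months past dose 2 is Φ(z(coverage/87.6) − 7/SD). The mean month cancels. With z(60/87.6) = 0.482 and z(80/87.6) = 1.361:

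| SD | at 60% | at 80% |
|---|---|---|
| 1.5 | 0.001% | 0.05% |
| 2 | 0.1% | 1.6% |
| 3 | 3.2% | 16.5% |

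First-dose coverage would be reached no later, so shares would be no larger. Booster coverage was only 65.1% on 14 June 2022, so an 80% booster cut-off had not been reached.

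**The case against.** The strongest reply is that an interval between two doses exists only for people who had both. Reading (a) is then natural, and uptake is already covered by the primary outcome, (i) and (ii). On that view, counting non-receipt within 7 months changes the question from spacing to timely uptake. Much of this stands. Reading (a) is the natural one, it is immune to a pure difference in completion, and the redefined outcome is not. But (a) is still truncated by the calendar end of follow-up and leaves out everyone still waiting, so it needs at least a stated risk set and minimum follow-up.

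The illustration is also open to challenge. Smokers' timing, the SD, the 4-month floor and the exponential wait are assumptions. The model implies that 39% to 61% of two-dose recipients pass 7 months, which the documents neither support nor refute. It ties the booster to time since dose 2 alone. The introduction describes a phased rollout; if boosters followed calendar availability, a later dose 2 would itself shorten the interval and 1.00 would not be the right benchmark. Adjustment for age and area may absorb part of any shift. The sizes are therefore illustrative only.

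The phrase allowing a later end date could lengthen follow-up. That moves the 31 October cut-off but does not remove it. Whether the coverage cut-offs are meant for (iii) and (iv) is unclear; the text neither includes nor exempts them by name.

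**Conclusion.** The concern holds for the supplied text. As written, (iii) and (iv) can be analysed in several ways, each distorted by the fixed end of follow-up or by how non-receipt is handled. The bias in the relative risk for (iv) can take either sign, provided dose timing or completion differs by tobacco use. Among both-dose recipients, the illustrative range for a one-month shift is 0.74–0.93 or 1.06–1.22 against a true 1.00, resting on the assumed inputs above.

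Four stronger conclusions that a reader might draw are not supported:

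- That the result for (iv) is known to be biased in a particular direction or by a particular amount. The documents give no timing or completion by smoking status.
- That the redefined outcome always returns 1.00. It does so for timing shifts, but not when completion differs.
- That the plan has no such rules anywhere. The Supplementary Appendix may contain them.
- That the main result is at risk. The primary outcome and (i) and (ii) involve no interval.

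**What to change.** For (iii) and (iv), restrict to recipients of the earlier dose given at least 7 months before the actual end of follow-up (about 31 October 2021 if it ends on 31 May 2022). Analyse *next dose not received within 7 months* with the same Poisson model, or use time to next dose with administrative censoring. Label the outcome timely receipt, and report the interval among both-dose recipients beside it as descriptive. Run the infection sensitivity analyses already planned on the same definition, because some non-receipt of a booster follows from the infection guidance the plan describes. Do not apply the 60% and 80% cut-offs to these two outcomes; otherwise, report the number eligible at each and say which dose coverage means. If the Supplementary Appendix already has such rules, bring them into the main text.

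This uses vaccination dates and infection data already planned. The costs are:

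- **Excluded or censored late vaccinees.** In the illustration the share is 1 − Φ((10.1 − mean)/SD): under 0.1% to 8% at SD 1.5 and about 4% to 24% at SD 3, for mean month 5 to 8.
- **A narrower population.** The estimate is conditional on having the earlier dose by the cut-off.
- **Overlap with (ii).** In the calibrated illustration 43–57% of those counted as delayed have no booster by the end of follow-up. A raised relative risk must therefore be read as delay and non-completion together.

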In this study, we will examine the association between tobacco use and COVID-19 vaccine uptake and between-dose spacing. Given conflicting results of previous studies, we expect to observe an association between tobacco use and vaccination uptake and dose-spacing, but the direction of the effect is unclear. We will expand current knowledge by examining two forms of tobacco use in Finland -smoking and smokeless tobacco use (snus)- and by analysing the spacing between vaccine doses. We will use data from nationally representative surveys in Finland linked to vaccination registries, which reduces the risk of selection and information bias.

Methods

The study protocol has been written in close accordance with the Strengthening the Reporting of Observational Studies in Epidemiology (STROBE) statement for cohort studies²⁷

Study design

The study design is a cohort study of nationally representative health surveys linked to COVID-19 vaccination data derived from the Finnish National Vaccination Register, using a unique personal identification number assigned to all residents in Finland.

Setting and participants

We will use data from two FinSote Surveys, which are cross-sectional population health surveys in Finland.

Participants in the FinSote 2018 Survey were adults aged 20 years and over derived from the Population Register of Statistics Finland, which comprises all residents in Finland. This sampling frame includes people living in institutions and military conscripts.²⁸ The survey

was based on stratified random sampling, one stratum for each 19 counties. In 2017, 3300 people were invited to participate from 18 research areas (2300 adults aged 20-74 and 1000 adults aged 75+, total sample size 59400). Data was collected between October 2, 2017, and March 3, 2018. Participants received a self-administered questionnaire in Finnish, Swedish, English or Russian, which could be returned on paper or filled in electronically. The participation rate was 45%, resulting in a total of 26422 participants.²⁸ Participants were asked for consent for registry linkage, resulting in an analytical sample of 14736 subjects.

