We will examine two forms of tobacco use: smoking and smokeless tobacco (snus) use. We will assess smoking status with the following question: Do you smoke currently (cigarettes, cigars or pipe)? (a) yes, daily, (b) occasionally, (c) not at all, (d) I have never smoked. We will create a categorical variable with the following categories: never smokers, former smokers, current occasional smokers and current daily smokers.

We will assess snus use with the following question: Do you currently use any of the following products? Snus (Swedish type moist stuff) (a) yes, daily, (b) occasionally, (c) not at all, (d) I have never used. We will create a categorical variable with the following categories: never users, former users, current users (daily and occasional combined). Data on smoking status is available for all participants, while data on snus use was available for participants aged 20-74 years old.

Potential confounders

We will adjust for several potential sociodemographic confounders: age, sex, marital status, educational tertile, and participation in social activities. All variables will be analysed at baseline. We will define marital status as those married or in a registered relationship or cohabiting versus those separated or divorced, widowed or single. We will calculate educational tertiles for each survey year using the years of education reported in the question “How many years altogether have you attended school or studied full time?”. We will analyse participants’ mother tongue using data from national registries and will categorise it into three categories: Finnish, Swedish and other. We will measure participation in social activities with a question about participation in the activities of any club, association, hobby group or religious or spiritual community. We will categorise participation into the following: no participation, occasional and active.

Potential mediators

We will take the incidence of COVID-19 infections into account (see below). We will obtain data on confirmed COVID-19 cases from the Finnish National Infectious Disease Register maintained by the Finnish Institute for Health and Welfare. Confirmed COVID-19 cases will be defined as those cases with a positive SARS-CoV-2 RT-PCR, either informed by a laboratory or by a physician as a record of an ICD-10 code U07.1 (which requires a positive SARS-CoV-2 RT-PCR). Reporting of COVID-19 positive cases was mandatory for laboratories and physicians throughout the study period.

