FinSote surveys 2018 and 2020 are based on a stratified random sample design that represents the Finnish population. However, non-participation in the survey could potentially introduce nonresponse bias if participants are systematically different from non-participants. For this purpose, we will take into account the complex survey design in all analyses and use the inverse probability weights (IPW) created by the Finnish Institute for Health and Welfare using a model with register-based data for the whole sample on age, sex, marital status, educational level, mother tongue and place of residence. The IPW method allows correcting for survey non-participation and the weighting factor of each participant is a combination of the inverse of the participation probability and the sampling probability. Hence, the set of weighted coefficients represents the Finnish population.³⁴

Information bias

The risk of information bias from measurement error of the exposure and confounders is inherent to most population health surveys. However, our data is almost entirely collected before assessment of the outcome, reducing the possibility that the exposure is affected by the occurrence of the outcome (i.e. that COVID-19 vaccination affects tobacco use). COVID-19 vaccination in Finland started on December 27, 2020, with a focus on health and residential care workers. The number of doses available in the first months was limited, so it is unlikely that participants from FinSote 2020 received the vaccination before the data collection. As sensitivity analyses, we will carry out the same analyses but excluding participants who have received a vaccination dose prior to February 8, 2021, when the data collection of FinSote 2020 ended. In addition, smoking status was collected relatively close to the COVID-19 vaccination, reducing (although not excluding it completely) the risk of exposure misclassification.

The COVID-19 vaccination has been implemented nationally by public providers, meaning that all COVID-19 vaccines provided have been registered in the Finnish National Vaccination Register. We estimate the risk of loss to follow-up and information bias of the outcome to be close to zero.

Study size

The sample size was determined by the available data from FinSote surveys 2018 and 2020. We consider it not necessary to provide a sample size calculation.

Quantitative variables

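### Tobacco use is described as measured close to vaccination, but about one third of the linked sample answered some three years before rollout, and no planned analysis separates the two survey waves

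*Combined protocol and SAP*

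**What the plan says.** The sentence at issue is under Bias, Information bias: "smoking status was collected relatively close to the COVID-19 vaccination". It goes on to say that this reduces the risk of exposure misclassification without ruling it out. It does not distinguish the two surveys.

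Setting and participants gives the dates. For FinSote 2018, "Data was collected between October 2, 2017, and March 3, 2018". FinSote 2020 fieldwork ran from September 14, 2020 to February 8, 2021. Follow-up starts on December 27, 2020 and ends on May 31, 2022 or the latest available date.

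The same section gives the sizes. For FinSote 2018, "The participation rate was 45%, resulting in a total of 26422 participants"; linkage then needed separate consent, "resulting in an analytical sample of 14736 subjects". For FinSote 2020 the analytical sample is 28,199, all linked.

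On covariates, Potential confounders says "All variables will be analysed at baseline" and does not define baseline. The covariate vector in equation 1 (Statistical methods) is "sex, age, marital status, years of education, mother tongue and participation in social activities", to which fixed effects for wellbeing area are added. Survey wave is not in the model. It is used only to cut the education tertiles.

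**The concern.** Someone who smoked in late 2017 and quit in 2019 is a former smoker at rollout but is analysed as a current smoker. If such people take up vaccination at a rate nearer that of former smokers, the contrast between current and never smokers shrinks. The same survey dates apply to snus use. A reader of the Information bias section would not learn that this affects a third of the sample.

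Nothing in the plan would reveal it. Effect modification covers age, sex and education. The sensitivity analyses cover infection status, doses received before February 8, 2021, complete cases, and follow-up cut at 60% and 80% coverage. None is by wave or limited to 2020.

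Two related gaps follow from pooling. The waves differ in calendar time and in selection through linkage consent, and equation 1 has no term for either. In addition, if baseline means the survey date, a FinSote 2018 participant enters the model about three years younger than at rollout, while a FinSote 2020 participant enters at nearly the right age.

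**Working it through.** **Reproducing the plan's figures.** The 2018 frame is described as "2300 adults aged 20-74 and 1000 adults aged 75+, total sample size 59400" from 18 areas: 3,300 × 18 = 59,400, and 26,422/59,400 = 44.5%, stated as 45%. For 2020, 2,800 × 22 = 61,600, and 28,199/61,600 = 45.8%, stated as 46%. Both agree.

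**Interval from exposure to rollout and to end of follow-up** (days/365.25, dates from Setting and participants):

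| Wave | To December 27, 2020 | To May 31, 2022 |
|---|---|---|
| FinSote 2018, first day | 1,182 days = 3.24 years | 1,702 days = 4.66 years |
| FinSote 2018, last day | 1,030 days = 2.82 years | 1,550 days = 4.24 years |
| FinSote 2020, first day | 104 days = 0.28 years | 624 days = 1.71 years |
| FinSote 2020, last day | 43 days after rollout | 477 days = 1.31 years |

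**Share of the sample.** 14,736/(14,736 + 28,199) = 14,736/42,935 = 34.3%, unweighted. The plan weights all analyses but does not say how the weights combine across waves. If each wave's weights sum to the population, the 2018 share is 50%. If the 2018 weights are not rescaled after consent loss (14,736/26,422 = 55.8% linked), it is 0.558/(1 + 0.558) = 35.8%.

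**Attenuation.** The documents give neither a quit rate nor an expected RR, so these inputs are assumptions: true RR for current smoking 0.90, RR for former smokers 0.97 to 1.00, and a fraction m = 10% to 30% of the 2018 current smokers having quit. Then

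RR(2018) = (1 − m) × 0.90 + m × RR(former)

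- Low end: 0.90 × 0.90 + 0.10 × 0.97 = 0.907, so 0.007/0.10 = 7% of the association is lost in that wave.
- High end: 0.70 × 0.90 + 0.30 × 1.00 = 0.930, so 30% is lost in that wave.

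Pooling with equal smoking prevalence in the two waves:

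- 34.3% share: 0.343 × 0.907 + 0.657 × 0.90 = 0.902, and 0.343 × 0.930 + 0.657 × 0.90 = 0.910. About 2% to 10% of the association is lost.
- 50% share: 0.5 × 0.907 + 0.5 × 0.90 = 0.9035, and 0.5 × 0.930 + 0.5 × 0.90 = 0.915.

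**A second set of assumptions.** Take uptake of 88% in non-users and 80% in users, so a true RR of 0.80/0.88 = 0.909. Let 5% to 30% of 2018 users quit and 1% of non-users start. The 2018-wave RR is (0.95 × 0.80 + 0.05 × 0.88)/(0.99 × 0.88 + 0.01 × 0.80) = 0.8040/0.8792 = 0.914 at the low end and 0.8240/0.8792 = 0.937 at the high end. The pooled RR is 0.911 to 0.919, or 0.912 to 0.923 with a 50% share.

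**Omitting wave from the model.** Under no true effect, assume user prevalence of 16% to 18% in 2018 against 12% to 14% in 2020, and uptake of 90% to 93% against 87% to 88%. Pooling without a wave term then gives a spurious RR of 1.001 to 1.008.

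**Age.** The midpoint of 2018 fieldwork is 3.03 years before rollout and that of 2020 fieldwork is 0.08 years before. If age is taken at the survey, it is therefore understated by about 3 years in one wave and 0.1 year in the other. With a linear age term, a wave indicator absorbs this near-constant shift. With the splines that the plan may select, or in the age-stratified results, it does not.

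**The case against.** The protocol says only that measurement was relatively close, and it concedes that misclassification remains. The sentence is accurate for FinSote 2020, which is two thirds of the unweighted sample. This stands: the fault is that one hedged sentence covers both waves, not that the plan denies the problem.

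The size is assumed and small where it counts. The 7% to 30% loss is confined to the 2018 wave, while the plan presents one pooled model, whose RR moves from 0.90 to at most 0.910 unweighted. The bias from leaving out wave is smaller still. This also stands. A reader might infer that the main result is seriously biased, but the documents contain nothing to support that.

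A reader might also infer that age is wrong by three years for the 2018 wave. The documents do not establish this. Baseline is undefined, it could mean December 27, 2020, and exact variables are deferred to an appendix not available here. Age at survey is the more natural reading, no more than that.

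Finally, a wave term might be taken as a cure for stale exposure. It is not: it shifts the level of uptake between waves and leaves misclassified people where they are. Only by-wave or 2020-only results address that.

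What remains is that the closeness statement fails for one wave and that no listed analysis would show the consequence. The planned exclusion of people vaccinated before February 8, 2021 guards against vaccination affecting reported tobacco use, which is a different problem.

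**Conclusion.** The concern holds in a limited form. The closeness statement is true of FinSote 2020 and untrue of FinSote 2018, whose tobacco data are 2.8 to 3.2 years old at rollout and 4.2 to 4.7 years old on May 31, 2022. The likely effect is attenuation: modest in the pooled estimate (0.90 to between 0.902 and 0.910 unweighted, up to 0.915 with a 50% share) and larger within the 2018 wave (0.907 to 0.930).

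These ranges rest on assumed quit rates and RRs, on equal smoking prevalence in the waves, and on quitters having the uptake of former smokers. The direction is probable rather than certain, and the true size cannot be found from the documents. The omitted wave term and the undefined baseline are gaps in specification, not demonstrated biases. This is an inexpensive improvement that should be made. It does not invalidate the pooled analysis.

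**What to change.** 1. In Information bias, give the interval from exposure measurement to rollout for each wave, and limit the closeness statement to FinSote 2020.
2. Report the primary outcome (at least two doses) by wave, and name a FinSote 2020-only sensitivity analysis (28,199 people). Keep the pooled analysis primary.
3. Add a survey-wave indicator to equation 1 to absorb differences in calendar time and in linkage consent (55.8% of 2018 participants linked, against all of the 2020 analytical sample). State that it does not correct stale exposure.
4. Define baseline, and compute age at December 27, 2020 for both waves.

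The cost is one covariate, one recoded variable and one subset run, with no new data. The 2020-only run has about one third fewer people (34.3%), so wider intervals. Its fieldwork also overlaps the rollout by 43 days, an overlap the 2018 wave does not have. It should therefore be combined with the exclusion, already planned, of people vaccinated before February 8, 2021.
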